Safety Parameters	The rate of neurostimulator device and procedure-related adverse events (AEs), Serious Adverse Events (SAEs) from informed consent through study exit will be reported.
Exploratory Endpoints	This study does not have any pre-defined endpoints but may include ad-hoc exploratory endpoint(s) to explore the relationship between metrics and clinical outcomes and/or to evaluate the effects of any recommendations made on outcomes.

¹ Extension Cohort: up to 300 enrolled subjects that consent to extend ENVISION study participation to approximately 48 months

	Exploratory endpoint(s) will be intended to generate hypotheses for future studies. Consequently, no correction for multiple testing will be performed for exploratory endpoint(s). Any exploratory endpoint(s) will be clearly identified as such in study reports, as applicable.
Follow-up Schedule	
Study assessments will be required, as appropriate, at the following time points:
 
 • Enrollment Visit (Day 0) • 1-Month Post-Enrollment Visit (30 days \pm 10 days) • 3-Month Post-Enrollment Visit (90 days \pm 10 days) • 12-Month Post-Enrollment Visit (365 days \pm 30 days) • Extension Cohort only: 24-Month Post-Enrollment Visit (730 days \pm 30 days)¹ • Additional Study Visit for SCS device related activities (e.g. SCS trial, end of SCS trial, IPG implant, IPG Activation, reprogramming, revision, etc.) or as needed for study. 
 ◦ Extension Cohort only: Additional Study Visits at 36 months (1095 days \pm 60 days) and 48 months (1460 days \pm 60 days) post enrollment
Participant Duration	The study duration for up to 300 enrolled subjects in the Extension Cohort ¹ is expected to be approximately 48 months. The study duration for the remaining subjects is expected to be 12 months.
Inclusion Criteria	
Subjects must meet all inclusion criteria, as outlined below:
 
 IC1. Study candidate is planning to receive or has received a commercially approved Boston Scientific neurostimulation system for pain, per local directions for use (DFU) IC2. Subject signed a valid, ENVISION IRB-approved informed consent form in English IC3. 18 years of age or older when written informed consent is obtained IC4. Is willing and able to comply with completing protocol required assessments and evaluations

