Data collected up to the point of subject withdrawal, lost to follow-up, or until subject deletes the mobile app and/or ends data transmission by removing and returning the wrist-worn biosensor and/or sleep sensor (for subjects enrolled under protocol ver. A and B) may be used for study analysis in accordance with applicable regulations. Subjects can stop data transmission by deleting the mobile app from their phone. Subjects can end wrist-worn biosensor transmission by removing the device and returning to the study site. Subjects enrolled under protocol Ver A and B can end sleep sensor transmission by removing the device and returning to the study site.

9.3. [REDACTED]

- [REDACTED]
- [REDACTED]
- [REDACTED]
- [REDACTED]
- [REDACTED]
- [REDACTED]
- [REDACTED]
- [REDACTED]
- [REDACTED]
- [REDACTED]

9.4. [REDACTED]

- [REDACTED]

9.5. *End-of-Study Definition & Plan*

A clinical trial is considered completed when participants are no longer being examined or the last participant's last study visit has occurred.

When each subject enrolled in the Extension Cohort reaches 36 months post-enrollment (maximum 1155 days post-enrollment) or withdraws, the subject exits the study and ends study participation. If the subject is implanted, the subject may continue to use the neurostimulator system per the applicable Directions for Use and should be followed according to standard, routine medical care.

When each enrolled subject who is not enrolled in the Extension Cohort completes the 12-Month Visit or withdraws, the subject exits the study and ends study participation. If the subject is implanted, the subject may continue to use the neurostimulator system per the applicable Directions for Use and should be followed according to standard, routine medical care.

10. Study Methods

10.1. [REDACTED]

[REDACTED]

10.2. *Study Candidate Screening*

Subjects' eligibility for the study will be assessed based on study Inclusion and Exclusion criteria. Subjects who have provided informed consent and who have been determined to not meet all eligibility requirements will be withdrawn.

10.3. *Informed Consent*

Written Informed Consent must be obtained for all patients who are potential study candidates. Study candidates will be asked to sign the Informed Consent form before any study-specific tests or procedures are performed.

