10.9. Additional Study Visit(s)

Subjects may have additional study visits for SCS device related activities (e.g. SCS trial, end of SCS trial, IPG implant, IPG Activation, reprogramming, revision, etc.) or as needed for study. These visits may be combined with required study visits if protocol windows allow. If they are combined required study visit requirements and additional study visits requirements must be completed however duplicate information should not be collected.

Please refer to Data Collection Table for additional data collection and/or assessments. If a subject has an SCS Trial and/or IPG Implant while participating in the study additional data collection forms will be completed at the Start of the SCS Trial, End of SCS Trial, IPG Implant and/or IPG Activation visits.

Subjects should bring their phone with mobile app and watch to these visit(s) and may be asked to respond to questions and/or questionnaires, submit voice recording/responses, log information such as pain, complete body map drawings, complete fitness assessments, and/or review notifications and/or recommendations on the mobile app during these visit(s). Assessments should be performed at the beginning of the visit.

10.9.1 Extension Cohort Only: Additional Study Visits at 36 and 48 months post enrollment

For Extension Cohort subjects only, additional study visit may be completed 36 and 48 Months post enrollment to allow the subject to complete study participation.

Subjects in the Extension Cohort should bring their phone with mobile app and watch to these optional visits. The wrist-worn biosensor and sleep sensor, as applicable for subjects enrolled under protocol A and B, will be returned to the site and mobile app needs to be deleted for the subject's phone at the end of this visit. Subjects may keep the commercially available Remote Control provided for the study however the subject needs to delete the mobile app to stop transmission of SCS data.

All required assessments, as outlined in the Data Collection Table, should be performed at the beginning of the visit.

10.10. *Study Completion*

An enrolled subject may complete participation in one of several ways:

- Subjects not in the Extension Cohort who complete the 12-Month Post Enrollment Visit.
- Subjects in the Extension Cohort who
 - Complete an Additional Study Visit Day 1095 ± 60 days post enrollment
 - Complete an Additional Study Visit Day 1460 ± 60 days post enrollment

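### ENVISION section 9.5 takes every Extension Cohort subject out of the study at 36 months (day 1155 at the latest), so the 48-month follow-up set out in the synopsis, 10.9.1 and 10.10 cannot be reached

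*Combined protocol and SAP*

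**What the plan says.** Two sets of statements on the Extension Cohort stand in the current ENVISION protocol (version of June 20, 2022).

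**Exit at 36 months.** Section 9.5, End-of-Study Definition & Plan: "When each subject enrolled in the Extension Cohort reaches 36 months post-enrollment (maximum 1155 days post-enrollment) or withdraws, the subject exits the study". The sentence goes on to say that study participation ends there.

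**Participation to about 48 months.**
- Synopsis footnote 1 defines the cohort as "up to 300 enrolled subjects that consent to extend ENVISION study participation to approximately 48 months".
- The synopsis row on participant duration says the duration for this cohort "is expected to be approximately 48 months. The study duration for the remaining subjects is expected to be 12 months".
- The synopsis follow-up schedule lists Extension Cohort visits at 36 months (1095 ± 60 days) and at 48 months (1460 ± 60 days).
- Section 10.9.1 says that an "additional study visit may be completed 36 and 48 Months post enrollment to allow the subject to complete study participation", and calls these visits optional: "Subjects in the Extension Cohort should bring their phone with mobile app and watch to these optional visits".
- Section 10.10 gives three completion routes for the cohort. The first is "Complete an Additional Study Visit Day 1095 ± 60 days post enrollment". The second is the corresponding visit at day 1460 ± 60, and the third is reaching a maximum of 1520 days.

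Study exit also closes the safety observation period. The synopsis safety row says: "Serious Adverse Events (SAEs) from informed consent through study exit will be reported". Section 17.4 requires investigators to report until a subject's participation ends.

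**The concern.** Section 9.5 makes exit at month 36 apply to each Extension Cohort subject, with withdrawal as the only alternative. The other sections treat month 36 as one possible end point and month 48 as another. A site that follows a subject to month 48 under 10.10 therefore keeps that subject in the study beyond the exit in 9.5. A site that applies 9.5 never reaches the 48-month visit.

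What is at stake is the length of observation. Take, as an illustration, a serious adverse event on day 1300 in a subject who wishes to continue. Under 10.10 it falls within participation, is reportable and enters the event rate. Under 9.5 the subject left the study at least 1300 − 1155 = 145 days earlier and is in routine care. The same event would be counted or missed according to the section applied. The 48-month assessments are exposed in the same way.

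**Working it through.** The check is visit-window arithmetic. No sample-size or power formula applies.

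**Inputs**
- 36-month visit: day 1095 ± 60 (synopsis follow-up schedule; 10.10)
- 48-month visit: day 1460 ± 60 (synopsis follow-up schedule; 10.10)
- Latest exit in 9.5: day 1155
- Latest participation in 10.10: day 1520
- Cohort size: up to 300 (synopsis footnote 1)

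**Step 1. Reproduce the two stated maxima** (target day plus window).
- 1095 + 60 = 1155, the maximum in 9.5.
- 1460 + 60 = 1520, the maximum in 10.10.

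Both reproduce exactly. Each maximum is the upper edge of a different visit window, so they are not two roundings of the same limit.

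**Step 2. Compare the windows.**

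| Visit | Opens | Closes |
|---|---|---|
| 36 months | 1095 − 60 = 1035 | 1155 |
| 48 months | 1460 − 60 = 1400 | 1520 |

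**Step 3. Measure the gap.**
- From the 9.5 limit to the opening of the 48-month window: 1400 − 1155 = 245 days.
- Between the two maxima: 1520 − 1155 = 365 days.

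The windows do not overlap. A subject who stays as long as 9.5 permits has been out of the study for 245 days when the 48-month window opens. Neither the window allowance nor the word approximately in the synopsis can bridge that gap.

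**Step 4. Test each 10.10 route against 9.5.**
- Completion at the day 1095 ± 60 visit is compatible with 9.5.
- Completion at the day 1460 ± 60 visit is impossible under 9.5.
- Reaching day 1520 is impossible under 9.5.

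Two of the three routes are closed.

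**The case against.** The strongest reply is that the plan already allows what the concern complains of. Section 10.10 accepts the 36-month visit as completion, and 10.9.1 makes both late visits optional. Even if 9.5 were deleted, one subject could finish at month 36 and another at month 48, so differing follow-up is built in. A site that completes everyone at month 36 breaches neither 9.5 nor 10.10. This stands, and it narrows the point: 9.5 does not create the variation in follow-up, but it removes the longer option.

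It also stands that 300 is a cap on the cohort and not a count of people affected. Subjects who would stop at month 36 anyway lose nothing. The number who would continue is not stated, and because the data collection table is redacted, the content of the 48-month assessments cannot be listed. The documents do not show that sites have in fact read the text differently.

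One can add that the study has no predefined endpoints or formal hypotheses, and that 9.5 may simply be a sentence not updated when 48 months was introduced. The first is correct and limits the consequence to observation time. The second is plausible but is inference, and a sentence left behind would still be a rule in force.

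Redaction of 9.3, 9.4 and 10.1 does not remove the conflict. Section 9.5 and the 10.10 routes are printed in full, and 9.5 carries no condition.

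**Conclusion.** The concern holds. The current text contains two incompatible ends of participation for the Extension Cohort: day 1155 in 9.5 and day 1520 in 10.10, which are 365 days apart. Followed as written, 9.5 makes the 48-month visit unreachable and ends safety observation up to 365 days earlier than 10.10 permits.

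The effect falls on subjects who would continue past month 36, within a cohort of at most 300. No retention assumption is made and no person-time total is claimed. The conclusion rests only on the printed day counts and on 9.5 being unconditional. It touches follow-up length and adverse event observation time, not any hypothesis test, power or alpha. Since study exit defines the period over which event rates are reported, this is more than a slip in wording and needs to be resolved. Which duration is right is for the sponsor to say.

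**What to change.** Choose one end of participation for the Extension Cohort and make every entry agree with it.

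- **If 48 months is intended:** change 9.5 to 48 months with a maximum of day 1520, and state in 10.10 that the day 1095 ± 60 visit completes participation only for subjects who do not continue.
- **If 36 months is intended:** restate the synopsis duration row, footnote 1 and follow-up schedule, together with 10.9.1 and 10.10, to 36 months with a maximum of day 1155. Check the consent wording, since footnote 1 describes consent to about 48 months.

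A related editorial point: 10.9.1 covers two visits but asks for device return and app deletion at the end of a single unspecified one. Tying this to the subject's final visit would match the closing paragraph of 10.10.

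The cost is a wording amendment with the IRB review that section 14.3 requires. The first option edits two sections. The second edits three synopsis entries and two sections and adds the consent check. Neither adds patients or procedures.

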10.8. Extension Cohort Only: 24-Month Post Enrollment Visit (730 days ± 30 days)

Subjects in the Extension Cohort should bring their phone with mobile app and watch to this visit.

All required assessments, as outlined in the Data Collection Table, should be performed at the beginning of the visit.

10.9. Additional Study Visit(s)

Subjects may have additional study visits for SCS device related activities (e.g. SCS trial, end of SCS trial, IPG implant, IPG Activation, reprogramming, revision, etc.) or as needed for study. These visits may be combined with required study visits if protocol windows allow. If they are combined required study visit requirements and additional study visits requirements must be completed however duplicate information should not be collected.

Please refer to Data Collection Table for additional data collection and/or assessments. If a subject has an SCS Trial and/or IPG Implant while participating in the study additional data collection forms will be completed at the Start of the SCS Trial, End of SCS Trial, IPG Implant and/or IPG Activation visits.

Subjects should bring their phone with mobile app and watch to these visit(s) and may be asked to respond to questions and/or questionnaires, submit voice recording/responses, log information such as pain, complete body map drawings, complete fitness assessments, and/or review notifications and/or recommendations on the mobile app during these visit(s). Assessments should be performed at the beginning of the visit.

10.9.1 Extension Cohort Only: Additional Study Visits at 36 and 48 months post enrollment

For Extension Cohort subjects only, additional study visit may be completed 36 and 48 Months post enrollment to allow the subject to complete study participation.

Subjects in the Extension Cohort should bring their phone with mobile app and watch to these optional visits. The wrist-worn biosensor and sleep sensor, as applicable for subjects enrolled under protocol A and B, will be returned to the site and mobile app needs to be deleted for the subject's phone at the end of this visit. Subjects may keep the commercially available Remote Control provided for the study however the subject needs to delete the mobile app to stop transmission of SCS data.

All required assessments, as outlined in the Data Collection Table, should be performed at the beginning of the visit.

10.10. *Study Completion*

An enrolled subject may complete participation in one of several ways:

- Subjects not in the Extension Cohort who complete the 12-Month Post Enrollment Visit.
- Subjects in the Extension Cohort who
 - Complete an Additional Study Visit Day 1095 ± 60 days post enrollment
 - Complete an Additional Study Visit Day 1460 ± 60 days post enrollment
 - Reach maximum 1520 days post enrollment.
- Subjects who withdraw, die, or become lost to follow up. Withdrawn subjects will not be replaced.
- Subjects who have a negative trial will not proceed to permanent implant, will complete the study 7-30 days post negative trial completion.
- Subjects who have a positive trial but do not proceed to permanent implant will be withdrawn.

Upon study completion subjects will be asked to return the wrist-worn biosensor and sleep sensor, as applicable for subjects enrolled under protocol A and B, to the site and deactivate the mobile app. Subjects may keep the commercially available Remote Control provided to allow data upload by connecting to their SCS device for the study.

10.11. *Source Documents*

It is preferable that original source documents are maintained, when available. In lieu of original source documents, certified copies are required to be maintained. A certified copy is a copy (irrespective of the type of media used) of the original record that has been verified (i.e., by a dated signature or by generation through a validated process) to have the same information, including data that describe the context, content, and structure, as the original. Source documentation includes but is not limited to those items noted in Table 10.11-1.

Data collected on Mobile app wrist-worn biosensor, sleep sensor is collected directly so will be the source.

Table 10.11-1: Source Documentation Requirements

Requirement	Disposition
Hospital records and/or clinical and office charts including the evidence of but not limited to inclusion/exclusion criteria, informed consent, procedures, exams, SCS System procedure(s) and devices used, evaluations, health economic assessments, laboratory results, medications, assessment of adverse events.	Retained at study site
Assessments and questionnaires	Retained at study site and/or electronic data collection platform/EDC
Imaging (Fluoroscopy)	Retained at study site
Medical Records	Retained at study site
SCS data	Electronic data collection platform/EDC

11. Statistical Considerations

11.1. *Endpoints*

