Subjects who meet all of the following criteria (see Table 8.2-1) may be given consideration for inclusion in this clinical investigation, provided no exclusion criterion (see Section 8.3) is met.

Table 8.2-1: Inclusion Criteria

Inclusion Criteria	IC1. Study candidate is planning to receive or has received a commercially approved Boston Scientific neurostimulation system for pain, per local directions for use (DFU)
	IC2. Subject signed a valid, ENVISION IRB-approved informed consent form in English
	IC3. 18 years of age or older when written informed consent is obtained
	IC4. Is willing and able to comply with completing protocol required assessments and evaluations
	[REDACTED]
	[REDACTED]

8.3. *Exclusion Criteria*

Subjects who meet any one of the following criteria (Table 8.3-1) cannot be included in this study or will be excluded from this clinical study.

Table 8.3-1: Exclusion Criteria

Exclusion Criteria	[REDACTED]
EC4.	Has any pain-related diagnosis, medical/psychological condition or external factors that, in the investigator's medical judgment, might confound reporting of study outcomes (e.g. history of pelvic pain, anginal pain, chronic migraine, involved in litigation, workmen's compensation)
	[REDACTED]

9. Subject Accountability

9.1. *Point of Enrollment*

The point of enrollment is when subject signs and dates the valid, IRB-approved ENVISION informed consent form. No study-related activities can take place until the ENVISION informed consent form is signed.

9.2. *Withdrawal*

All subjects enrolled in the clinical study (including those withdrawn from the clinical study) shall be accounted for and documented. If a subject withdraws from the clinical investigation, the reason(s) shall be reported. If such withdrawal is due to problems related to device safety or performance, the investigator shall ask for the subject's permission to follow his/her status/condition outside of the clinical study.

A subject is considered lost-to-follow-up after 3 unsuccessful contact attempts have been made to reach the subject (including those who relocate but cannot be transferred to another participating site). Staff at the participating site should make a good faith effort to contact the

subject with three documented communication attempts, at least one of which must be in writing, sent via a traceable method to inform the subject that the device must be programmed per standard of care with commercially approved settings.

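### An ENVISION Extension subject can complete by elapsed time alone, with no scheduled adverse-event enquiry after month 24 in the visible text

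*Combined protocol and SAP*

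**What the plan says.** All references are to the ENVISION Cohort appendix.

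- **Section 10.10** lists the ways an Extension subject completes: "Complete an Additional Study Visit Day 1095 ± 60 days post enrollment"; "Complete an Additional Study Visit Day 1460 ± 60 days post enrollment"; or "Reach maximum 1520 days post enrollment". The third names no visit or contact. Subjects outside the Extension complete at the 12-month visit.
- **Section 10.9.1** says that an "additional study visit may be completed 36 and 48 Months post enrollment to allow the subject to complete study participation", and that subjects "should bring their phone with mobile app and watch to these optional visits".
- **Section 10.8** sets the 24-month visit at day 730 ± 30. It is the last scheduled visit that the body text does not call optional.
- **Section 9.5** ends Extension participation when the subject reaches 36 months, at most day 1155. This too is worded as reaching a time, not attending a visit.
- **The synopsis** puts the 36- and 48-month visits in a list of time points at which assessments are required where appropriate, nested under additional visits. Its safety paragraph covers device- and procedure-related adverse events and ends: "Serious Adverse Events (SAEs) from informed consent through study exit will be reported".
- **Section 9.2** gives the rule for loss: "A subject is considered lost-to-follow-up after 3 unsuccessful contact attempts have been made to reach the subject".

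**The concern.** The safety rate is the one result ENVISION commits to report, since it has no pre-defined endpoints. That rate runs to study exit, and exit can be reached by the calendar alone.

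A subject who skips both optional visits passes day 1520 and is complete. Nothing in the visible text prompts the three contact attempts that would class a silent subject as lost, because no late contact is due. After month 24, serious events, related adverse events and device deficiencies are recorded only if the subject comes in for unscheduled care or the site otherwise learns of them.

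The later years are what the Extension adds, and they are the part with the weakest ascertainment. Missed events would lower a reported rate whether it is per subject or per unit of time.

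**Working it through.** **1. Reproduce the plan's exit days.** From the visit windows in 10.10: 1460 + 60 = 1520, the day in 10.10. 1095 + 60 = 1155, the day in 9.5. Both reproduce. Each is the upper end of a visit window, but the two sections stop at different windows.

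**2. Gap from the 24-month visit to exit.** The visit may fall on day 700, 730 or 760. It is assumed that adverse events are asked about there.

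| 24-month visit | Gap to day 1520 (10.10) | Gap to day 1155 (9.5) |
|---|---|---|
| Day 700 | 820 days (2.25 years) | 455 days (1.25 years) |
| Day 730 | 790 days (2.16 years) | 425 days (1.16 years) |
| Day 760 | 760 days (2.08 years) | 395 days (1.08 years) |

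At the nominal date the gap is 790/1520 = 52% of follow-up under 10.10 and 425/1155 = 37% under 9.5.

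**3. Illustration of the effect on a person-time rate.** Let f be the share of Extension subjects who take the no-visit route, c the share of their later events still captured, and E the exit day. With a constant hazard, and all other subjects followed and fully ascertained to day E:

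observed/true = (1 − f) + f × [730 + c × (E − 730)] / E

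The documents give neither f nor c, so both are assumptions. With E = 1520:

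| f | c = 0 | c = 0.5 |
|---|---|---|
| 10% | 0.948 | 0.974 |
| 25% | 0.870 | 0.935 |
| 50% | 0.740 | 0.870 |
| 100% | 0.480 | 0.740 |

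At f = 50% and c = 0: 0.5 + 0.5 × 730/1520 = 0.740, an understatement of 26%. At c = 0.5: 0.5 + 0.5 × 1125/1520 = 0.870, or 13%.

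With E = 1155 and f = 50%: 0.5 + 0.5 × 730/1155 = 0.816 (18%) at c = 0, and 0.5 + 0.5 × 942.5/1155 = 0.908 (9%) at c = 0.5.

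**4. Sensitivity to how the others exit.** 10.10 also allows completion at the 36-month visit. If half of 300 subjects take the no-visit route to day 1520 and the other half complete at day 1095, the unascertained share is 150 × 790 / (150 × 1520 + 150 × 1095) = 118,500/392,250 = 30%.

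**The case against.** The strongest reply is that much of the relevant plan cannot be seen. Section 10.1 and the general statistical methods in 11.2 are redacted, and the Data Collection Table is not in the public text. A contact schedule or a rule for time at risk may sit there. The synopsis can also be read as requiring the late visits. This stands as a limit on the claim. It does not remove the point, because 10.10 would still count a subject who missed both visits as complete, and the visible follow-up schedule shows no other fixed time point after month 24. The listed uses of the mobile app do not include asking about adverse events.

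There are also safeguards. Section 17.4 makes sites report serious events, related events and device deficiencies through the end of participation. Additional visits exist for reprogramming and revision, and subjects are established patients of the practice. Some late events will be captured, so zero capture is a worst case. These duties still depend on the site learning of the event.

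Three stronger readings are tempting, and the documents do not support them:

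- **The gap is always over two years.** That holds under 10.10 only. Under 9.5 it is about 13 to 15 months.
- **The unascertained time is counted as event-free follow-up.** No visible text says whether the rate is per subject or per person-time, or where time at risk ends.
- **Missed lead or battery failures lower the adverse-event rate directly.** Under notes 8 and 9 of section 17.2, lead migration, failures and malfunctions go on the device deficiency form and become adverse events only if they cause one.

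**Conclusion.** The point holds in limited form. As written, the completion rule lets an Extension subject exit as completed with no scheduled adverse-event enquiry in the visible text after day 730 ± 30. The gap is 760 to 820 days if 10.10 governs and 395 to 455 days if 9.5 governs. A safety rate reported through study exit may be understated as a result.

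The size is not known. The 26% and 13% figures assume that half the subjects take the route, a constant hazard, a person-time rate, others followed to day 1520, and late capture of none or half. They describe Extension subjects only; a rate pooled with 12-month subjects would be affected differently. A reader might also infer that retention will be overstated, but the visible plan names no retention measure. What can be said is that the count of completed subjects may include some who were not contacted late.

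ENVISION is exploratory, with no formal hypotheses, so this threatens no test. It is a cheap improvement to the result that the study does promise.

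**What to change.** 1. Reconcile the exit day and the status of the 36- and 48-month visits across the synopsis and sections 9.5, 10.9.1 and 10.10.
2. In 10.10, replace completion by elapsed time with completion at an exit contact, by telephone if need be, that asks about adverse events and device deficiencies by the reconciled exit day. 10.10 already asks subjects to return devices and deactivate the app at completion, so the enquiry can be joined to that step.
3. If three documented attempts at that contact fail, class the subject as lost to follow-up, in line with 9.2.
4. State the denominator of the safety rate. For any rate that uses time at risk, end it at the last contact at which adverse events were asked about.

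The cost is one call for at most 300 subjects and a slightly lower reported completion figure. A subject who skipped both late visits would be asked to recall up to 820 days under 10.10 or 455 under 9.5, so minor events may still be missed. Reports should say how many subjects had only the exit call. Item 4 adds no site work.
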